6.1.2 Disease Parameters

Measurable Disease

Measurable lesions are defined as those that can be accurately measured in at least one dimension (longest diameter to be recorded)

as \geq 20 mm by chest x-ray, as \geq 10 mm with CT scan, or \geq 10 mm with calipers by clinical exam. All tumor measurements must be recorded in millimeters.

NOTE: Tumor lesions that are situated in a previously irradiated area are not considered measurable.

Malignant Lymph Nodes

To be considered pathologically enlarged and measurable, a lymph node must be

\geq 15 mm in short axis when assessed by CT scan (CT scan slice thickness recommended to be no greater than 5 mm). At baseline and in follow-up, only the short axis will be measured and followed.

Non-measurable Disease

All other lesions (or sites of disease), including small lesions (longest diameter $<$ 10 mm or pathological lymph nodes with \geq 10 to $<$ 15 mm short axis), are considered non-measurable disease. Bone lesions, leptomeningeal disease, ascites, pleural/pericardial effusions, lymphangitis cutis/pulmonitis, inflammatory breast disease, and abdominal masses (not followed by CT or MRI), are considered as non-measurable. Non-measurable also includes lesions that are $<$ 20 mm by chest x-ray.

NOTE: Cystic lesions that meet the criteria for radiographically defined simple cysts should not be considered as malignant lesions (neither measurable nor non-measurable) since they are, by definition, simple cysts.

'Cystic lesions' thought to represent cystic metastases can be considered as measurable lesions, if they meet the definition of measurability described above. However, if non-cystic lesions are present in the same patient, these are preferred for selection as target lesions.

Target Lesions

All measurable lesions up to a maximum of 2 lesions per organ and 5 lesions in total, representative of all involved organs, should be identified as target lesions and recorded and measured at baseline. Target lesions should be selected on the basis of their size (lesions with the longest diameter), be representative of all involved organs, but in addition should be those that lend themselves to reproducible repeated measurements. It may be the case that, on occasion, the largest lesion does not lend itself to reproducible measurement in which circumstance the next largest lesion which can be measured reproducibly should be selected.

A sum of the diameters (longest for non-nodal lesions, short axis for nodal lesions) for all target lesions will be calculated and reported as the baseline sum diameters. If lymph nodes are to be included in the sum, then only the short axis is added into the sum. The baseline sum of the diameters will be used as reference to further characterize any

objective tumor regression in the measurable dimension of the disease.

Non-target Lesions

All other lesions (or sites of disease) including any measurable lesions over and above the 5 target lesions should be identified as non-target lesions and should also be recorded at baseline. Measurements of these lesions are not required, but the presence or absence of unequivocal progression of each should be noted throughout follow-up.

6.1.3 Methods for Evaluation of Disease

All measurements should be taken and recorded in metric notation using a ruler or calipers. All baseline evaluations should be performed as closely as possible to the beginning of treatment and never more than 4 weeks before randomization.

The same method of assessment and the same technique must be used to characterize each identified and reported lesion at baseline and during follow-up. Imaging-based evaluation is preferred to evaluation by clinical examination unless the lesion(s) being followed cannot be imaged but are assessable by clinical exam.

Clinical Lesions

Clinical lesions will only be considered measurable when they are superficial (e.g., skin nodules and palpable lymph nodes) and ≥ 10 mm in diameter as assessed using calipers (e.g., skin nodules). In the case of skin lesions, documentation by color photography, including a ruler to estimate the size of the lesion, is recommended.

Chest X-ray

Lesions on chest x-ray are acceptable as measurable lesions when they are clearly defined and surrounded by aerated lung. However, CT is preferable.

Conventional CT and MRI

This guideline has defined measurability of lesions on CT scan based on the assumption that CT slice thickness is 5 mm or less. If CT scans have slice thickness greater than 5 mm, the minimum size for a measurable lesion should be twice the slice thickness. MRI is also acceptable in certain situations (e.g. for body scans).

Use of MRI remains a complex issue. MRI has excellent contrast, spatial, and temporal resolution; however, there are many image acquisition variables involved in MRI which greatly impact image quality, lesion conspicuity, and measurement. Furthermore, the availability of MRI is variable globally. As with CT, if an MRI is performed, the technical specifications of the scanning sequences used should be optimized for the evaluation of the type and site of disease. Furthermore, as with CT, the modality used at follow-up must be the same as was used at baseline and the lesions should be measured/assessed on the same pulse sequence. It is beyond the

scope of the RECIST guidelines to prescribe specific MRI pulse sequence parameters for all scanners, body parts, and diseases. Ideally, the same type of scanner should be used and the image acquisition protocol should be followed as closely as possible to prior scans. Body scans should be performed with breath-hold scanning techniques, if possible.

PET-CT

At present, the low dose or attenuation correction CT portion of a combined PET-CT is not always of optimal diagnostic CT quality for use with RECIST measurements. However, if the site can document that the CT performed as part of a PET-CT is of identical diagnostic quality to a diagnostic CT (with IV and oral contrast), then the CT portion of the PET-CT can be used for RECIST measurements and can be used interchangeably with conventional CT in accurately measuring cancer lesions over time. Note, however, that the PET portion of the CT introduces additional data which may bias an investigator if it is not routinely or serially performed.

FDG-PET

The role of FDG-PET response in this disease requires additional study. As such, new lesions identified on FDG-PET imaging may not be used to determine disease progression. FDG-PET will be interpreted visually (uptake above mediastinal blood pool will be interpreted as positive). Standardized uptake values (SUV) will be recorded in identified lesions for purposes of evaluation of response to treatment.

For correlative imaging studies, EORTC criteria will be used for the assessment of response to treatment by PET in solid tumors.

1. Progressive metabolic disease (PMD) to be classified as an increase in FDG tumor SUV of greater than 25% within the tumor region defined on the baseline scan, visible increase in the extent of FDG tumor uptake (20% in the longest dimension) or the appearance of new FDG uptake in metastatic lesions.
2. Stable metabolic disease (SMD) would be classified as an increase in tumor FDG SUV of less than 25% or a decrease of less than 15% and no visible increase in extent of FDG tumor uptake (20% in the longest dimension).
3. Partial metabolic response (PMR) would be classified as a reduction of a minimum of $15 \pm 25\%$ in tumor FDG SUV after one cycle of chemotherapy, and greater than 25% after more than one treatment cycle.

Reporting would need to be accompanied by adequate and disclosed reproducibility measurements from each centre. An empirical 25% was found to be a useful cut-off point, but there is a need for a reproducibility analysis to determine the appropriate cut-offs for statistical significance. A reduction in the extent of the tumor FDG uptake is not a requirement for partial metabolic response.

4. Complete metabolic response (CMR) would be complete resolution of FDG uptake within the tumor volume so that it was indistinguishable from surrounding normal tissue.

Ultrasound

Ultrasound is not useful in assessment of lesion size and should not be used as a method of measurement. Ultrasound examinations cannot be reproduced in their entirety for independent review at a later date and, because they are operator dependent, it cannot be guaranteed that the same technique and measurements will be taken from one assessment to the next. If new lesions are identified by ultrasound in the course of the study, confirmation by CT or MRI is advised. If there is concern about radiation exposure at CT, MRI may be used instead of CT in selected instances.

Endoscopy, Laparoscopy

The utilization of these techniques for objective tumor evaluation is not advised. However, such techniques may be useful to confirm complete pathological response when biopsies are obtained or to determine relapse in trials where recurrence following complete response (CR) or surgical resection is an endpoint.

Tumor Markers

Tumor markers alone cannot be used to assess response. If markers are initially above the upper normal limit, they must normalize for a patient to be considered in complete clinical response. Specific guidelines for both CA-125 response (in recurrent ovarian cancer) and PSA response (in recurrent prostate cancer) have been published [JNCI 96:487-488, 2004; J Clin Oncol 17, 3461-3467, 1999; J Clin Oncol 26:1148-1159, 2008]. In addition, the Gynecologic Cancer Intergroup has developed CA-125 progression criteria which are to be integrated with objective tumor assessment for use in first-line trials in ovarian cancer [JNCI 92:1534-1535, 2000].

Cytology, Histology

These techniques can be used to differentiate between partial responses (PR) and complete responses (CR) in rare cases (e.g., residual lesions in tumor types, such as germ cell tumors, where known residual benign tumors can remain)

6.1.4 Response Criteria

6.1.4.1 Evaluation of Target Lesions

Complete Response (CR)

Disappearance of all target lesions. Any pathological lymph nodes (whether target or non-target) must have reduction in short axis to < 10 mm.

Partial Response (PR)

At least a 30% decrease in the sum of the diameters of target lesions, taking as reference the baseline sum diameters

Progressive Disease (PD)

At least a 20% increase in the sum of the diameters of target lesions, taking as reference the smallest sum on study (this includes the baseline sum if that is the smallest on study). In addition to the relative increase of 20%, the sum must also demonstrate an absolute increase of at least 5 mm.

NOTE: The appearance of one or more new lesions is also considered progression, See Section [6.1.4.3](#)

Stable Disease (SD)

Neither sufficient shrinkage to qualify for PR nor sufficient increase to qualify for PD, taking as reference the smallest sum diameters while on study. (Note: a change of 20% or more that does not increase the sum of the diameters by 5 mm or more is coded as stable disease)

To be assigned a status of stable disease, measurements must have met the stable disease criteria at least once after study entry at a minimum interval of 8 weeks.

6.1.4.2

Evaluation of Non-Target Lesions

Complete Response (CR)

Disappearance of all non-target lesions. All lymph nodes must be non-pathological in size (< 10 mm short axis).

Non-CR/Non-PD

Persistence of one or more non-target lesion(s).

Progressive Disease (PD)

Appearance of one or more new lesions and/or unequivocal progression of existing non-target lesions (see Section [6.1.4.3](#)). Unequivocal progression should not normally trump target lesion status. It must be representative of overall disease status change, not a single lesion increase.

When the patient also has measurable disease, there must be an overall level of substantial worsening in non-target disease such that, even in the presence of SD or PR in target disease, the overall tumor burden has increased sufficiently to merit discontinuation of therapy. A modest "increase" in the size of one or more non-target lesions is usually not sufficient to qualify for unequivocal progression status. The designation of overall progression solely on the

basis of change in non-target disease in the face of SD or PR of target disease will therefore be extremely rare.

When the patient only has non-measurable disease, the increase in overall disease burden should be comparable in magnitude to the increase that would be required to declare PD for measurable disease: i.e., an increase in tumor burden from “trace” to “large”, an increase in nodal disease from “localized” to “widespread”, or an increase sufficient to require a change in therapy.

Although a clear progression of “non-target” lesions only is exceptional, the opinion of the treating physician should prevail in such circumstances, and the progression status should be confirmed at a later time by the review panel (or Principal Investigator).

6.1.4.3 Evaluation of New Lesions

The appearance of new lesions constitutes Progressive Disease (PD).

A growing lymph node that did not meet the criteria for reporting as a measurable or non-measurable lymph node at baseline should only be reported as a new lesion (and therefore progressive disease) if it:

- a) increases in size to ≥ 15 mm in the short axis, or
- b) there is new pathological confirmation that it is disease (regardless of size).

New effusion or ascites that appears during treatment should only be reported as a new lesion (and therefore progressive disease) if it has cytological confirmation of malignancy.

6.1.4.4 Evaluation of Best Overall Response

The best overall response is the best response recorded from the start of the treatment until disease progression/recurrence or non-protocol therapy (taking as reference for progressive disease the smallest measurements recorded since the treatment started). The patient’s best response assignment will depend on the achievement of both measurement and confirmation criteria.

For Patients with Measurable Disease (i.e., Target Disease)

Target Lesions	Non-Target Lesions	New Lesions*	Best Overall Response	Remarks
CR	CR	No	CR	≥ 4 wks. Confirmation
CR	Non-CR/Non-PD***	No	PR	
CR	Not evaluated	No	PR	
PR	Non-PD***/not evaluated	No	PR	
SD	Non-PD***/not evaluated	No	SD	Documented at least once ≥ 8 wks. from study entry
PD	Any	Yes or No	PD	No prior SD, PR or CR
Any	PD**	Yes or No	PD***	
Any	Any	Yes	PD	

* See RECIST 1.1 manuscript for further details on what is evidence of a new lesion.

** In exceptional circumstances, unequivocal progression in non-target lesions may be accepted as disease progression.

***PD in non-target lesions should not normally trump target lesion status. It must be representative of overall disease status change, not a single lesion increase. Please refer to the Evaluation of Non-Target Lesions – Progressive Disease section for further explanation.

NOTE: Patients with a global deterioration of health status requiring discontinuation of treatment without objective evidence of disease progression at that time should be reported as “*symptomatic deterioration*.” Every effort should be made to document the objective progression even after discontinuation of treatment.

6.1.4.5 Duration of Response

Duration of Overall Response

The duration of overall response is measured from the time measurement criteria are met for CR or PR (whichever is first recorded) until the first date that recurrent or progressive disease is objectively documented (taking as reference for progressive disease the smallest measurements recorded since the treatment started).

The duration of overall CR is measured from the time measurement criteria are first met for CR until the first date that progressive disease is objectively documented.

Duration of Stable Disease

Stable disease is measured from the start of the treatment until the criteria for progression are met, taking as reference the smallest measurements recorded since the treatment started, including the baseline measurements.

To be assigned a status of stable disease, measurements must have met the stable disease criteria at least once after study entry at a minimum interval of 8 weeks.

7. Study Parameters

7.1 Therapeutic Parameters

1. Prestudy scans and x-rays used to assess all measurable or non-measurable sites of disease must be done within 4 weeks prior to randomization.
2. Prestudy CBC (with differential and platelet count) and chemistries should be done \leq 2 weeks before randomization.
3. Pregnancy testing (if applicable) should be done within 2 weeks of randomization.

	Prior to Randomization (Baseline) ¹	Day 1 of Each Treatment Cycle	Every 8 weeks	Post Treatment ⁹
Tests and Observations				
Assessment of medical history ²	X	X		X
Physical Examination ^{2,13}	X	X		X
Pulse, Blood Pressure ²	X	X		
Height	X			
Weight and BSA calculation ²	X	X		
Performance Status ²	X	X		
Tumor Measurements ²	X		X	X
Adverse Events Assessment ²	X	X		X ¹⁰
Pill Count/Diary		X ¹¹		
Laboratory and Imaging Studies				
CBC with Differential and Platelets ³	X	X		
Serum Electrolytes and Liver Function Tests ^{2,4}	X	X		
Coagulation studies (PT, INR, aPTT)	X	X ¹²		
Serum or Urine Pregnancy Test ⁵	X			
Radiographic Studies ^{2,6}	X		X	X
Image Submissions ⁸	X		X	
Biological Specimen Submissions ⁷ .				
MANDATORY: Pre-trial FFPE tumor ⁷	X			
Peripheral Blood, ACD vacutainer	X			

1. Baseline requirements must be assessed prior to randomization as outlined in Section 3. Blood tests must be performed \leq 2 weeks prior to randomization. CT and/or MRI must be performed \leq 4 weeks prior to randomization.
2. After Cycle 1, the following assessments may be scheduled with a +/- 3 day window; Assessment of medical history, Physical Examination, Pulse and Blood Pressure, Weight/BSA calculation, Performance Status, Tumor Measurements, Adverse Events Assessment, Serum Electrolytes and Liver Function, Radiographic Studies, including Images.
3. CBCs (with differential and platelet count) which includes WBC, ANC, Platelets, Hgb and Hct required for protocol therapy must be done $<$ 24 hours prior to the treatment cycle.
4. Serum Electrolytes and Liver Function Tests include Na+, K+, Cl-, bicarbonate, BUN, creatinine, glucose, Mg++, AST, ALT, alkaline phosphatase, total protein, albumin, total bilirubin and direct bilirubin.

Rev. Add3

5. All females of childbearing potential must have a negative [blood test or urine test] within 14 days prior to study registration to rule out pregnancy..
6. CT of the chest, abdomen and pelvis. If only MRI of the abdomen and/or pelvis is available, this can be substituted for CT of the abdomen and/or pelvis but CT of the chest should still be obtained. Contrast agents should be administered unless otherwise contraindicated. PET-CTs can be used, so long as the CT portion is of the same diagnostic quality and includes IV and oral contrast. The same screening technique used at baseline should be used for all subsequent follow-up scans. Even though dosing schedules are different in the two treatment arms, radiographic imaging should be obtained every 8 weeks by calendar while on protocol treatment.
7. Submit as outlined in Section [11](#). Mandatory diagnostic tumor tissue must be submitted for central diagnostic review and classification and ancillary laboratory research studies. Peripheral blood is to be submitted per patient consent. Submit to within 4 weeks following randomization.

Rev. Add3

8. Baseline and subsequent imaging studies should be submitted to the IROC Imaging Core Facility for central image banking < 4 weeks after each imaging time point. In addition to the CT/MRI scans, baseline and subsequent [¹⁸F]-FDG PET scans, ⁶⁸Ga-PET scans and octreotide scans, if performed, should be submitted.
9. After completion of protocol treatment, monitor for adverse events for 30 days following discontinuation of treatment. Monitoring for survival, and scans should be performed every 3 months until patient is 2 years from randomization. Monitoring for survival and scans should be completed every 6 months if patient is 3-5 years from randomization. Once the patient progresses, adverse event assessments and scans no longer need to be performed but patients should be followed for survival (every 3 months until 2 years from randomization, every 6 months if 3-5 years from randomization).
10. Adverse Events Assessment is required 30 days after last dose of protocol therapy.
11. Note this is only required for patients randomized to Arm A.
12. Repeat coagulation studies only need to be followed in patients on anti-coagulant therapy and may be obtained within a +/- 3 day window along with serum electrolytes and liver function studies.
13. Baseline physical exam should be performed within 14 days of randomization.

8. Drug Formulation and Procurement

Capecitabine, temozolomide, cisplatin and etoposide will all be obtained commercially.

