5.1.2 Cisplatin (or Carboplatin) and Etoposide—Arm B

Cycle = 21 days (+/- 2 days)

CBC will be monitored prior to day 1 of drug administration.

Premedication with ondansetron (or other 5HT3 antagonist) and dexamethasone prior to each chemotherapy administration (days 1-3) is required. Additional antiemetics, analgesics and anxiolytics may be used per the discretion of the treating physician. Pre- and post-treatment hydration may be administered per institutional standards.

If the treating physician chooses to use Aprepitant, when given once daily for 14 days as a 100 mg capsule with an oral contraceptive containing 35 mcg of ethinyl estradiol and 1 mg of norethindrone, this decreased the AUC of ethinyl estradiol by 43% and decreased the AUC of norethindrone by 8%. Women of childbearing potential using pregnancy contraception that includes ethinyl estradiol should not receive Aprepitant for the treatment of nausea/delayed emesis. Patients may change to a different method of contraception if they wish to use Aprepitant.

- Cisplatin 25 mg/m² daily x 3 days (days 1-3) to be administered per institutional guidelines.

OR

- Carboplatin target AUC of 5 once on day 1 to be administered per institutional guidelines

AND

- Etoposide 100mg/m² daily x 3 days (days 1-3) to be administered per institutional guidelines.

Continue treatment until patient develops disease progression (as defined by Section [6.1.4](#)) or unacceptable toxicity.

NOTE: Treatment will be administered on an outpatient basis unless local institutional standard practice requires inpatient administration.

NOTE: CALVERT FORMULA FOR CARBOPLATIN DOSING:

Total Dose (mg) = (target AUC) x (GFR + 25)

For the purposes of this protocol, the GFR is considered to be equivalent to the creatinine clearance.

Round up any creatinine \leq 0.6 mg/dL, to 0.6 mg/dL

Glomerular Filtration Rate (GFR) Estimation: Calculated creatinine clearance of \geq 50 cc/min using the Cockcroft-Gault formula:

Males:
$$\frac{(140 - \text{Age in years}) \times \text{Actual Body Weight in kg}}{72 \times \text{Serum Creatinine (mg/dL)}}$$

Females: Estimated creatinine clearance for males x 0.85

With the Calvert formula, the total (final) dose of carboplatin is calculated in mg, not mg/m².

DO NOT exceed a dose of 150 mg per AUC or cap at 750 mg/AUC5.

NOTE: Choice of platinum agent will be per treating physician discretion. Once a platinum agent is picked, no changes are allowed.

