5.3.4 Cisplatin or Carboplatin Dose Modifications

- **Dose reductions:** For non-hematologic grade 3 and 4 AEs (except for nausea and vomiting as well as AEs unrelated to treatment) the dose should be reduced according to the Cisplatin/Carboplatin Dose Level Table at the discretion of the investigator. Dose reductions for treatment day (or within 2 days of treatment) ANC and platelet counts should also be made according to the Dose Level Table below.

NOTE: The etoposide will be held if platinum is held until a decision is made to skip platinum for the current cycle so that all drugs are kept on the same schedule.

- **Discontinuation** Also, except for nausea and vomiting, if any of the same non-hematologic grade 3 and 4 AEs that are at least possibly related to platinum recur after two reductions for that AE, then platinum will be stopped.
- A patient's protocol treatment will be discontinued if more than 2 cumulative dose reductions are necessary or if patients are unable to restart platinum within 3 weeks of interruption. Dose reductions will be permanent. Missed doses will be made up once toxicity is resolved per guidelines below.
- All toxicity grades below are described using the NCI Common Terminology Criteria for Adverse Events (CTCAE) version 4.0.

Cisplatin Dose Level Table	
Dose Level	Dose in mg/m ² (days 1-3)
0	25
-1	20
-2	16

*Note this is a 20% dose reduction with each dose level.

Carboplatin Dose Level Table	
Dose Level	Dose in AUC (day 1)
0	5
-1	4

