Grade 2 ($>$ 1.5 - 3.0 x ULN)	Omit dose of cisplatin until resolved to CTCAE Grade \leq 1 or baseline, then - If resolved in \leq 7 days, then maintain dose level. - If resolved in $>$ 7 days, then ↓ 1 dose level.	Omit dose of carboplatin until resolved to CTCAE Grade \leq 1 or baseline, then - If resolved in \leq 7 days, then maintain dose level. - If resolved in $>$ 7 days, then ↓ 1 dose level.
Grade \geq 3 ($>$ 3.0 x ULN)	Discontinue study treatment.	Discontinue study treatment
INVESTIGATIONS – HEPATIC		
Blood Bilirubin ^b (for patients with Gilbert Syndrome these dose modifications apply to changes in direct bilirubin only) For patients with total bilirubin \geq grade 3, a CT scan or equivalent imaging procedure to exclude disease progression or potential other liver disease should be performed.		
Grade 1 ($>$ ULN – 1.5 x ULN)	Maintain dose level.	Maintain dose level
Grade 2 ($>$ 1.5 – 3.0 x ULN)	Omit dose of cisplatin until resolved to CTCAE Grade \leq 1, then - If resolved in \leq 7 days, then maintain dose level. - If resolved in $>$ 7 days, then ↓ 1 dose level.	Omit dose of carboplatin until resolved to CTCAE Grade \leq 1, then - If resolved in \leq 7 days, then maintain dose level. - If resolved in $>$ 7 days, then ↓ 1 dose level.
Grade 3 ($>$ 3.0 – 10 x ULN) or higher	Discontinue study treatment. NOTE: If CTCAE Grade 3 or 4 hyper-bilirubinemia is due to the indirect (non-conjugated) component only, and hemolysis as the etiology has been ruled out as per institutional guidelines (e.g. review of peripheral blood smear and haptoglobin determination), then ↓ 1 dose level and continue treatment at the discretion of the Investigator.	Discontinue study treatment. NOTE: If Grade 3 or Grade 4 hyperbilirubinemia is due to the indirect (unconjugated) component only, and hemolysis as the etiology has been ruled out as per institutional guidelines (e.g., review of peripheral blood smear and haptoglobin determination), then ↓ 1 dose level and continue treatment at the discretion of the investigator.
AST or ALT		

Worst Toxicity CTCAE v4.0 Grade (unless otherwise specified)	Recommended Dose Modifications to cisplatin any time during a cycle of therapy	Recommended Dose Modifications to carboplatin any time during a cycle of therapy
Grade 1 and 2 (up to 5.0 x ULN)	Maintain dose level.	Maintain dose level.

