Grade 3	Omit dose of cisplatin or carboplatin until resolved to CTCAE Grade \leq 1, then \downarrow dose level of cisplatin or carboplatin.	
Grade 4	Discontinue study treatment.	

NOTE: All of the above are general guidelines. The investigator may omit dose of drug, decrease dose level of drug, or remove any patient from study for any toxicity, if he/she believes that it is in the best interest of the patient.
 
If a patient requires a dose delay of > 21 consecutive days of cisplatin or carboplatin then the patient must be discontinued from the study treatment. Patients who discontinue from the study for a study-related adverse event or an abnormal laboratory value must be followed at least once a week for 3 weeks and subsequently at 3-week intervals, until resolution or stabilization of the event, whichever comes first, unless stated otherwise.
		

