5.3.5.2 Non-hematologic Toxicity

Gastrointestinal Toxicity, Nausea and Vomiting

All patients should receive antiemetics* to prevent nausea and vomiting. Steroids and 5-HT3 antagonists are required premedications but additional specific antiemetic therapy is left to the discretion of the treatment physician. If vomiting is severe, consider hospital admission and/or use of aprepitant if possible. Do not modify chemotherapy doses.

*Aprepitant, when given once daily for 14 days as a 100 mg capsule with an oral contraceptive containing 35 mcg of ethinyl estradiol and 1 mg of norethindrone, decreased the AUC of ethinyl estradiol by 43% and decreased the AUC of norethindrone by 8%. Women of childbearing potential using pregnancy contraception that includes ethinyl estradiol should not receive Aprepitant for the treatment of nausea/delayed emesis. Patients may change to a different method of contraception if they wish to use Aprepitant.

Hepatotoxicity

Bilirubin	Etoposide*
≤ 1.5 X ULN	100%
> 1.5 – 3.0 X ULN	50%
> 3.0 X - ≤ 5.0 ULN	30%
> 5 X ULN	Hold**

* Please note that the % dose administered is based on the original starting dose of etoposide (100 mg/m²). If patient is at dose level -1 or -2, % should be based on reduced dose the patient is currently on, not original dose.

** For bilirubin greater than 5 X ULN it is recommended not to use etoposide for that cycle but this is at the discretion of the treating physician. If holding, repeat labs on a weekly basis for

up to 3 weeks until total bilirubin is \leq 5 X ULN. The cisplatin dose should also be held if etoposide is held so that all drugs are kept on the same schedule. If bilirubin improves within 3 weeks to \leq 5 X ULN, then resume treatment and use reduced dose per table above. If bilirubin does not improve to \leq 5 X ULN within 4 weeks, discontinue protocol therapy.

Hypomagnesemia

Hypomagnesemia is not an indication for stopping therapy. Oral or parenteral magnesium supplementation is indicated for serum magnesium levels $<$ 1.5 mEq/L.

Allergic Reactions

Discontinue all protocol treatment promptly if \geq grade 3 anaphylaxis develops.

Suggested Management of Allergic Reaction:

In case of mild allergic symptoms (e.g., appearance of a localized or generalized pruritus), symptomatic treatment may be given (e.g., oral antihistamine or corticosteroids).

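### From cycle 2 the study calendar lets Arm B chemistries and liver tests be drawn up to 3 days after Day 1, too late for that cycle's etoposide bilirubin adjustment or a carboplatin omission

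*Combined protocol and SAP*

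**What the plan says.** The Section 7.1 calendar lists serum electrolytes and liver function tests under Day 1 of each cycle. Footnote 4 shows that the panel contains creatinine, AST, ALT and total and direct bilirubin. Footnote 2 relaxes the timing: "After Cycle 1, the following assessments may be scheduled with a +/- 3 day window", and its list includes this panel. Footnote 12, on coagulation tests for anticoagulated patients, says these "may be obtained within a +/- 3 day window along with serum electrolytes and liver function studies". Footnote 3 treats blood counts differently: "CBCs (with differential and platelet count) which includes WBC, ANC, Platelets, Hgb and Hct required for protocol therapy must be done" less than 24 hours before the cycle.

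Arm B (Section 5.1.2) gives carboplatin on day 1 only, or cisplatin on days 1-3, with etoposide on days 1-3. Three sets of rules use the chemistry results:

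- **Etoposide, Section 5.3.5.2.** The dose falls to 50% at bilirubin above 1.5 and up to 3.0 x ULN, and to 30% above 3.0 and up to 5.0 x ULN. Beyond that, "For bilirubin greater than 5 X ULN it is recommended not to use etoposide for that cycle", at the physician's discretion.
- **Platinum, Section 5.3.4.1.** Platinum is omitted until recovery for grade 2 creatinine or bilirubin and for grade 3 AST/ALT. Treatment stops for grade 3 or higher creatinine and for grade 4 AST/ALT. For grade 3 or higher bilirubin the entry reads "Discontinue study treatment. NOTE: If CTCAE Grade 3 or 4 hyper-bilirubinemia is due to the indirect (non-conjugated) component only", in which case (haemolysis excluded) a one-level reduction is allowed. The closing note says "All of the above are general guidelines".
- **Carboplatin dose, Section 5.1.2.** The Calvert formula is used, and "For the purposes of this protocol, the GFR is considered to be equivalent to the creatinine clearance".

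**The concern.** A window on both sides of Day 1 suits an assessment that only describes the patient. It does not suit a test whose result decides whether, or how much, drug is given that day. Arm B is front-loaded: all the platinum and etoposide is in by day 3, and all the carboplatin on day 1. A site that schedules by the calendar could comply fully and still see a raised bilirubin, AST/ALT or creatinine only after the doses it should have influenced. What is at stake is patient safety and whether the dose guidance can be applied in time.

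**Working it through.** The plan states no figure to reproduce. The check is day arithmetic plus a search for any other timing rule.

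**Step 1. Is pre-dose timing fixed elsewhere?**

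- Section 5.1.2 requires only a CBC before day 1.
- Sections 5.3.4 and 5.3.5 tie treatment-day values (or values within 2 days) to ANC and platelets only.
- Section 8.3.11.1 asks for BUN and creatinine before cisplatin, so that combination is covered.
- Sections 8.4.11.1 (carboplatin) and 8.5.11.1 (etoposide) name only blood counts.
- Section 8.2.11.7 asks for liver tests after each cycle, but it concerns temozolomide (Arm A).

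Not covered: Arm B bilirubin and AST/ALT with either platinum, and creatinine with carboplatin.

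**Step 2. Latest compliant draw.** Footnote 2 does not say whether the window runs from planned or actual Day 1. Early starts are prohibited (Section 5.3.1) and the Arm B cycle window is +/- 2 days, so a start within that window can slip by 0, 1 or 2 days. Counts are before any infusion due on the day of the draw.

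- From actual Day 1: 1 + 3 = Day 4. Given: 3 of 3 days (etoposide 3 x 100 = 300 mg/m²; cisplatin 3 x 25 = 75 mg/m²).
- From planned Day 1, start 1 day late: planned Day 4 is treatment day 3. Given: 2 of 3 days (200 and 50 mg/m²).
- From planned Day 1, start 2 days late: planned Day 4 is treatment day 2. Given: 1 of 3 days (100 and 25 mg/m²).
- Carboplatin: fully given in all three cases.

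**Step 3. Etoposide above the Section 5.3.5.2 table.** At dose level 0 the planned cycle is 300 mg/m². The table gives 300 x 0.50 = 150, 300 x 0.30 = 90, or a recommended 0. If n full-dose days precede the result and the table (fraction f) is followed afterwards, the excess is n x 100 x (1 - f) mg/m²:

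| Days given first (n) | >1.5-3.0 x ULN (f = 0.5) | >3.0-5.0 x ULN (f = 0.3) | >5 x ULN (f = 0, recommended) |
|---|---|---|---|
| 3 | 150 | 210 | 300 |
| 2 | 100 | 140 | 200 |
| 1 | 50 | 70 | 100 |

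**Step 4. Arm A.** Capecitabine is taken twice daily for 14 days, or 28 doses. At the latest draw, 2 to 6 doses have been taken (2/28 = 7%; 6/28 = 21%). Temozolomide is given on days 10-14, so 0 of 5 doses have been taken. Most of the cycle can still be adjusted.

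**The case against.** The strongest reply is that the platinum table in Section 5.3.4.1 is headed as applying at any time in a cycle and is graded on worst toxicity, so a result on Day 3 or 4 is usable. That stands for remaining and later platinum doses. It does not help a carboplatin dose given on day 1, or etoposide already infused.

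A second reply is that strict timing for counts and looser timing for chemistries is deliberate: Section 5.3.1 bases doses on non-hematologic adverse events in the previous cycle, and Section 5.2.2 counts abnormal laboratory findings as adverse events. The etoposide table, moreover, cannot be followed without a bilirubin. This shows that the authors expected results to be known, and many sites will draw early. But a silent rise is unknown until the sample is taken, and the calendar calls a late sample compliant.

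Third, the gap is narrow. Cisplatin creatinine is covered, and a site drawing it will probably run the whole panel. That is fair, but it does not cover carboplatin patients, and nothing requires the liver tests to be drawn at the same time.

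A reader might also infer that below 5 x ULN the proper etoposide dose is 0, so that the excess is always 300 mg/m². That comes from combining the platinum table with the rule in Section 5.3.4 that "The etoposide will be held if platinum is held until a decision is made to skip platinum for the current cycle". It reflects a separate mismatch between Sections 5.3.4.1 and 5.3.5.2, which changing the window would not resolve, so it is not counted here.

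**Conclusion.** The point holds as a low-cost patient-safety improvement. From cycle 2, a compliant Arm B draw can follow all of the cycle's carboplatin and 1 to 3 of 3 etoposide and cisplatin days. Measured against the Section 5.3.5.2 table alone, the largest case is 300 mg/m² of etoposide given where 150, 90 or a recommended 0 applies. This assumes dose level 0, a literal two-sided reading of footnote 2, and a result available no earlier than the day of the draw. The documents give no rate of such abnormalities at cycle start, so no patient count is offered.

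Four stronger readings are not supported:

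- The protocol does not require a late draw. The window is permissive, and a site that draws early meets every rule.
- No fixed limit is broken. The platinum table is described as guidance, and the etoposide hold is a recommendation.
- The Calvert dose need not be recalculated each cycle as far as the text goes; that would be an inference. The case for a current creatinine with carboplatin rests on the omission and discontinuation entries in Section 5.3.4.1.
- Nothing here affects power, alpha or the trial's conclusions.

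**What to change.** Amend footnote 2 so that, from cycle 2, serum electrolytes and liver function tests are resulted and reviewed within 3 days before (-3 to 0 days) the actual first dose of the cycle. Reword footnote 12 so that its mention of chemistries follows the same rule. Keep +/- 3 days for tumor measurements and imaging.

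Moving adverse event assessment and weight/BSA into the pre-dose window is an optional consistency edit. Sections 5, 5.3.1 and 5.3.5.2 already make dosing depend on them.

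The cost is two footnotes in an amendment, less scheduling freedom and an occasional repeat draw. A repeat is needed only when (days drawn before planned Day 1) + (days the start slips) exceeds 3. A sample on planned Day 1 survives a 3-day slip, and one taken the day before survives a 2-day slip. Any repeat can be taken with the CBC that footnote 3 already requires.
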